13. STUDY MEDICATION EXPOSURE

Exposure to study medication in days will be summarized for the FAS and PPAS.

The dates of first study medication administration and last study medication administration will be obtained from the eCRF Exposure form (EC). In the case of missing data on the eCRF, the diary data will be used to determine the first and last date of study medication. Interruptions and compliance are not considered for duration of exposure.

13.1. DERIVATIONS

- Overall duration of study treatment exposure (days) = End dose date of last study medication administration – Start dose date of first study medication administration + 1.

14. STUDY MEDICATION COMPLIANCE

Compliance to study medication will be presented for the FAS and PPAS.

Compliance with double-blind study medication will be calculated as the number of capsules taken (total dispensed – total returned and confirmed by e-diary entries) divided by the expected number of capsules expressed as a percentage.

Patients will take 2 capsules per day, from Day 1 to Day 112, regardless of treatment group. They will receive 70 capsules at each dosing visit (Days 1, 29, 57 and 85) and compliance for these visits will be determined by the number of capsules returned at the next visit (Days 29, 57, 85 and 113). The number of capsules dispensed and returned will be obtained from the Drug Accountability eCRF page and e-Diaries completed by patients. For patients who permanently stop the study medication, the last visit will be replaced by the date of study withdrawal.

Document: \\iedc-vnasc01\BIOSdata\Abivax\ABX464\FZA92720\Biostatistics\Documentation\SAP\ABX464-103_SAP_V2.0_10MAY2021

Author: [REDACTED] Version Number: 2.0
Version Date: 10May2021

Template No.: CS_TP_BS016 Revision 5

Reference: CS_WI_BS005

Effective Date: 01Apr2018

14.1. DERIVATIONS

- Compliance up to Week 8 will be calculated using:

$$\frac{\text{No.Capsules dispensed at Day 1} - \text{No.Capsules returned at Day 57}}{\text{Total expected number of capsules for the period (2 per day)}} \times 100$$

- Overall Compliance to study medication will be calculated as follows:

$$\frac{\text{Total number of Capsules taken from Day 1 to Day 112}}{\text{Total expected number of capsules for the period (2 per day)}} \times 100$$

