5.2.4. PER PROTOCOL ANALYSIS SET [PPAS]

The Per Protocol Analysis Set (PPAS) will include all patients in the FAS who do not have major PDs that would affect the evaluation of the primary efficacy endpoint. From a statistical analysis perspective, the reason(s) for exclusion of patients may be a PD or other factors affecting the primary efficacy outcome. PDs identified during the clinical conduct of the study, as authorized in the final PD log, will also be taken into consideration in the final assignment of patients to the analysis sets.

Reasons for exclusion are defined as:

- Insufficient essential efficacy data i.e. no MMS score at either Baseline or Week 8
- Non-compliance with the inclusion or exclusion criteria, including insufficient evidence of the study indication, i.e. MMS score < 5 (or MMS < for patients enrolled on original protocol) and endoscopy sub-score < 2 at screening
- Non-compliance with the study treatment up to Week 8 (< 80%)
- Intake of prohibited medication up to Week 8
- Non-compliance with time window up to Week 8 (+/- 7 days) (to be confirmed at CRT meeting)

Therefore, the following patients will be excluded from this Analysis Set:

- All patients excluded from the FAS.
- Patients with essential efficacy data missing or invalid:

CRITERION [5]: Insufficient Essential Efficacy Data

DEVIATION STATUS: Major.

NOTES:

Document: \\iedc-vnasc01\BIOSdata\Abivax\ABX464\FZA92720\Biostatistics\Documentation\SAP\ABX464-103_SAP_V2.0_10MAY2021

Author: [REDACTED]

Version Number:

2.0

Version Date:

10May2021

Template No.: CS_TP_BS016 Revision 5

Reference: CS_WI_BS005

Effective Date: 01Apr2018

- The primary efficacy variable is the change in MMS score from baseline to Week 8.
- This criterion will be tested using:
 - The subject's MMS scores, as captured on the MMS eCRF and obtained from raw.MMS.MMSSCR at Week 8.

- Patients with insufficient evidence of the study indication, i.e. ulcerative colitis:

CRITERION [6]: Insufficient Evidence of the Study Indication

DEVIATION STATUS: Major/No Major Impact, to be decided on a case-by-case basis at the final data review meeting.

NOTES:

- This criterion will be tested at Screening, and not meeting the following criteria will be captured on the IE eCRF by raw.IE.IECAT and IETESTCD, as well as on the MMS eCRF by raw.MMS.MMSSCR and raw.MMS.MMSMA:

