Day 1 (Baseline)	1	n/a	n/a
Day 8	8	6	10
Day 29	29	27	31
Day 57	57	53	61
Day 85	85	81	89
Day 113	113	109	117
Day 120 (EOS)	120	118	122

For details on the calculation of the study day, see Section 6.1. EOS visit only applies to all premature discontinued patients and patients not taking part in maintenance study. In case of early discontinuation, the patient will be encouraged to return to the study center for the End of Study (EOS) visit within a week after last dosing.

Document: \\ieedc-vnasc01\BIOSdata\Abivax\ABX464\FZA92720\Biostatistics\Documentation\SAP\ABX464-103_SAP_V2.0_10MAY2021

Author: [REDACTED]

Version Number:
Version Date:

2.0
10May2021

Template No.: CS_TP_BS016 Revision 5

Reference: CS_WI_BS005

Effective Date: 01Apr2018

- This criterion will be tested using:
 - The name and date of visit as captured on the Date of Visit (DOV) eCRF and obtained from raw.DOV.VISDAT.
 - The visit for the patient will be flagged only if the day of the actual visit is outside the lower or upper limit. It will be discussed during the BDR meeting whether only the Week 8 and Week 16 visit non-adherence should be regarded as a major deviation.
- Overall study treatment non-compliance (< 80%) up to Week 8:

CRITERION [15]: Treatment Non-Compliance

DEVIATION STATUS: Major/No Major Impact to be decided on a case-by-case basis at the final data review meeting.

NOTES:

- Treatment compliance will be handled as described in Section 14. A patient's compliance will be assessed by considering the number of capsules issued and returned at each visit, as well as the actual number of capsules taken as recorded in the e-diary by the patient.
- This criterion will be tested as follows:
 - Number of capsules dispensed and returned as captured on the DA eCRF and obtained from raw.DA.DAORRES4 and DAORRES5.
 - Number of capsules taken as recorded in the e-diaries.

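### The SAP's Week 8 compliance formula omits the Day 29 dispensing and return, so a fully adherent patient scores 50% and nobody treated through the Week 8 visit can reach the 80% per-protocol threshold

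*SAP*

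**What the plan says.** SAP 14 defines capsules taken as "total dispensed – total returned and confirmed by e-diary entries", divided by the number expected. On supply it states: "They will receive 70 capsules at each dosing visit (Days 1, 29, 57 and 85"). Each supply is assessed from what comes back at the next of Days 29, 57, 85 and 113. Patients take two capsules a day.

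SAP 14.1 then displays the Week 8 calculation. The numerator is "No.Capsules dispensed at Day 1" minus the number returned at Day 57. The denominator is the expected number for the period at two a day. No Day 29 quantity appears.

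The result feeds the per-protocol set. SAP 5.2.4 lists as a reason for exclusion "Non-compliance with the study treatment up to Week 8 (< 80"%). Criterion 15 in the same section, headed "Overall study treatment non-compliance (< 80%) up to Week 8", refers to Section 14 for the calculation. It also describes assessment by "considering the number of capsules issued and returned at each visit", together with the e-diary count. Its deviation status is "Major/No Major Impact to be decided on a case-by-case basis at the final data review meeting".

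The protocol agrees with the supply schedule: section 5.2.3 has drug dispensed at Day 29, and section 6.4 has used and unused blister cards brought back at every visit.

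**The concern.** The displayed formula covers only part of the drug flow in the first eight weeks but divides by the whole of it. It also subtracts the leftovers of the second supply from the size of the first.

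This is the only Week 8 compliance formula the SAP displays, and Criterion 15 points to the section that contains it. A programmer working from the derivations would produce a value that flags every patient treated through the Week 8 visit. It would also be blind to doses missed before Day 29. Two things are at stake:

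- The Week 8 compliance results for the FAS and the PPAS.
- Membership of the PPAS, and hence the PPAS versions of the primary analysis (SAP 15.1.3 and 15.1.4.1) and the secondary analyses (SAP 15.2).

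**Working it through.** The plan states no expected compliance value, so there is no figure to reproduce. The check applies the printed formula to the SAP's own schedule.

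**Inputs**
- Supply: 70 capsules at Day 1 and 70 at Day 29 (SAP 14).
- Returns: first supply at Day 29, second at Day 57 (SAP 14).
- Use: 2 capsules a day (SAP 14).
- Threshold: 80% up to Week 8 (SAP 5.2.4).
- Period: Day 1 to the day before the Week 8 visit. This is an assumption, because SAP 14.1 gives no end day. For a Day 57 visit, expected = 2 × 56 = 112.

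**Fully adherent patient, nominal visits**
- Days 1–28: 56 used, 70 − 56 = 14 returned at Day 29.
- Days 29–56: 56 used, 14 returned at Day 57.
- Printed formula: (70 − 14)/112 = 50.0%.
- With both supplies: (70 + 70 − 14 − 14)/112 = 112/112 = 100%.

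Both supplies contain 70, so 70 minus the Day 57 return is simply the use from the second supply. It is divided by the expectation for both.

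**Can anyone reach 80%?** At a Day 57 visit, 80% needs 0.8 × 112 = 89.6 capsules, and the numerator cannot exceed 70. The table varies the Week 8 visit over the ±7 days in SAP 5.2.4, with the Day 29 visit on Day 29:

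| Week 8 visit | Expected | Ceiling (nothing returned) | Fully adherent, printed formula |
|---|---|---|---|
| Day 50 | 98 | 70/98 = 71.4% | 42/98 = 42.9% |
| Day 53 | 104 | 70/104 = 67.3% | 48/104 = 46.2% |
| Day 57 | 112 | 70/112 = 62.5% | 56/112 = 50.0% |
| Day 61 | 120 | 70/120 = 58.3% | 64/120 = 53.3% |
| Day 64 | 126 | 70/126 = 55.6% | 70/126 = 55.6% |

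If the Day 29 visit also moves within its ±2 days and the Day 57 visit within ±4, full adherence scores from 44/104 = 42.3% (Days 31 and 53) to 68/120 = 56.7% (Days 27 and 61). Reaching 80% requires a period of at most 70/(2 × 0.8) = 43.75, that is 43 whole days. Even a Day 50 visit implies 49.

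**What the printed value responds to (Day 57 visit)**

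| Pattern | Printed formula | Both supplies |
|---|---|---|
| All doses taken | (70 − 14)/112 = 50.0% | (140 − 14 − 14)/112 = 100% |
| None in Weeks 1–4, all in Weeks 5–8 | (70 − 14)/112 = 50.0% | (140 − 70 − 14)/112 = 50.0% |
| All in Weeks 1–4, none in Weeks 5–8 | (70 − 70)/112 = 0% | (140 − 14 − 70)/112 = 50.0% |

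The first two patients cannot be told apart, and the last two have the same true compliance but score 50% and 0%. No rescaling of the printed value would repair this.

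**Sensitivity to the end of the period.** If the Day 57 dose is counted as well, full adherence scores (70 − 12)/114 = 50.9% and the ceiling is 70/114 = 61.4%.

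**The case against.** The strongest reply is that the SAP already contains the right rule. SAP 14 defines capsules taken from total dispensed and total returned, and Criterion 15 calls for counts at each visit plus the e-diary. The overall-compliance formula beside the faulty one is also consistent with SAP 14: 4 × 70 − 4 × 14 = 224 taken, against 2 × 112 = 224 expected. On this view the fault is one display line whose intent is recoverable. All of that is correct, but it makes the line an internal contradiction rather than a harmless one, because the displayed derivation is what would naturally be programmed.

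Second, exclusion is a case-by-case decision at a blinded meeting, where a flag on nearly every patient would be conspicuous. This stands: an empty PPAS does not follow automatically. Still, the flag would not help the meeting pick out the patients below 80%, and the Week 8 compliance summary has no comparable check.

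Third, the formula is not wholly uninformative, since it responds to use in Weeks 5–8. That is right. What it misses is use of the first supply, and at the 80% cut everyone treated through the Week 8 visit falls on the same side.

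Fourth, the end day of the period is an assumption. SAP 14 counts dosing from Day 1 to Day 112, whereas protocol 6.1 gives 113 days and protocol 7.1 continues treatment until Day 113; those passages should be reconciled. The choice does not alter the conclusion. Reading the period as 28 days would give 56/56 = 100%, but that conflicts with a figure labelled as running to Week 8 and using the Day 57 return.

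**Conclusion.** The concern holds. As printed, the Week 8 formula gives 50.0% for a fully adherent, on-schedule patient whose compliance is 100%. Its ceiling is 62.5% at a Day 57 visit and 71.4% at the earliest visit in the ±7-day window. No patient treated through the Week 8 visit can meet the 80% threshold.

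The 50.0% figure assumes nominal visit days, each supply's leftovers returned at the next dispensing visit, and a period ending the day before the Week 8 visit. The shortfall below 80% holds across the visit windows and for either end day.

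The reach is limited. FAS membership, the FAS primary analysis and the overall-compliance formula are unaffected. Patients who stop early have a shorter period and can pass: one withdrawn on Day 20 after taking 40 capsules scores (70 − 30)/40 = 100%, counting Day 20. The Week 8 compliance results would be wrong if the formula is programmed literally, and PPAS membership would rest on a flag that does not identify non-compliance. It should be fixed before the per-protocol set is assigned.

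**What to change.** Replace the Week 8 numerator in SAP 14.1 with (capsules dispensed at Day 1 + Day 29) minus (capsules returned at Day 29 + Day 57), confirmed against the e-diary. State the denominator explicitly as 2 × the number of days from Day 1 to the day before the Week 8 visit, or whichever end day the sponsor settles on, applied consistently. Keep the existing SAP 14 rule: "For patients who permanently stop the study medication, the last visit will be replaced by the date of study withdrawal". Full adherence then gives (140 − 28)/112 = 100%.

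The cost is one formula in the SAP and the matching program. No new data are needed, because dispensing and returns are already on the Drug Accountability eCRF page. No dose or clinical rule changes.

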15. EFFICACY OUTCOMES

15.1. PRIMARY EFFICACY

15.1.1. PRIMARY EFFICACY VARIABLE & DERIVATION

The primary efficacy variable is the reduction from baseline in MMS at Week 8 (Day 57).

The MMS will be obtained from the MMS eCRF page with raw.MMS.MMSSCR and confirmed by eDiary entries. The MMS ranges from 0 to 9 and is derived from the sum of 3 sub-scores ranging from 0 to 3 for stool frequency, rectal bleeding and mucosal appearance at endoscopy respectively, with a lower score indicating less severe or no ulcerative colitis (UC) (See APPENDIX 2). The MMS determined at screening will be used as baseline MMS, as MMS is not calculated at Day 1.

Change from baseline is described in Section 6.6.

Document: \\ieedc-vnasc01\BIOSdata\Abivax\ABX464\FZA92720\Biostatistics\Documentation\SAP\ABX464-103_SAP_V2.0_10MAY2021

Author: [REDACTED]

Version Number: 2.0
Version Date: 10May2021

Template No.: CS_TP_BS016 Revision 5

Reference: CS_WI_BS005

Effective Date: 01Apr2018

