1. INTRODUCTION AND STUDY RATIONALE

1.1. Ulcerative Colitis (UC)

1.1.1. Disease

Ulcerative colitis (UC) is a chronic inflammatory condition causing continuous mucosal inflammation of the colon without granulomas on biopsy, affecting the rectum and a variable extent of the colon in continuity, which is characterized by a relapsing and remitting course.

UC is a lifelong disease arising from an interaction between genetic and environmental factors, observed predominantly in the developed countries of the world.

The precise etiology is unknown and therefore medical therapy to cure the disease is not yet available.

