5.2.1. Screening Visit (Within 28 ± 3 days prior to Day 1)

The screening visit is within 4 Weeks (28 ± 3 days) prior to the first dosing, hence the maximum screening period is 31 days. However, patients can be randomized anytime within the screening window if all examinations are performed as per their schedule and results are available.

The patient will be informed about the general aspects of the study and will sign the screening informed consent form. The patient number will be allocated once the patient is screened in the ITRS. Only when consent has been given may further study procedures be carried out.

During the screening phase, the following assessments will be performed:

- Signed informed consent form;
- Demographic data: year of birth and gender;

- Disease extent (proctitis, left-sided or extensive), duration and disease activity, prior treatment and smoking status;
- Refractoriness to biologics (primary non-response or loss of response);
- Body weight and height;
- Medical history;
- Clostridium difficile (stool antigen and toxin), CMV (IgG and IgM), TB;
- Physical examination and vital signs;
- Hematology and Biochemistry including pregnancy test for all women of childbearing potential;
- 12 leads ECG;
- Sigmoidoscopy with rectal and sigmoidal (if the sigmoid is inflamed) biopsies (within 14 days prior to randomization/baseline); central read results must be available before randomization;
- Record endoscopy sub-score and transfer videos to central reader;
- Partial Modified Mayo Score (within a week prior to endoscopy) and Modified Mayo Score (once endoscopy is performed);
- Hand over the e-Diary to the patient and instruct the patient how to use it; e-Diary should be collected daily from screening to end of study;
- Record all medications received within 3 months prior to baseline and note if the medication is continuing;
- Record all UC medication without time limitation;
- Adverse Event reporting;
- Inclusion/exclusion criteria will be verified.

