5.2.2. Baseline (First dosing day / Day 1)

- Randomization: The Investigator needs to check the inclusion/exclusion criteria (central read of the endoscopy and patient's symptom score from e-diary) with respect to the procedures performed at screening visit and if applicable proceed with the patient randomization. Treatment numbers will be allocated at randomization via the IWRS and dispensed to the patient;
- IBD Questionnaire (as the patient's first procedure);
- Physical examination and vital signs;
- Body weight;
- 12 leads ECG;
- Population Pharmacokinetics blood samples at either 0.5, 1.5, 3h (and 6 h and/or 10 h if possible) or at 1, 2, 4h (and 8 h and/or 12 h if possible);
- Hematology and Biochemistry including blood pregnancy test for all women of childbearing potential, coagulation parameters and troponin;
- Blood sample for miR-124 (PAXgene® tube) and cytokines determination;
- Serum collection for patients with loss of response to previous biologics (i.e. neutralizing antibodies);
- Fecal calprotectin dosage;
- Partial Modified Mayo Score;
- Review the patient e-Diary;
- Adverse Events reporting;
- Dispense study treatment to patient and instruct how to take them (First dosing at site);
- Schedule next patient visits.

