 - The change from screening in Modified Mayo scores and Partial Mayo scores during the study.

In this mixed model, treatments and stratum will be fixed effects, subject will be random effect and baseline values of the respective measurements will be covariates. Other explanatory variables will also be allowed to be included in the model. To normalize eventual skewed distributions transformation of the data will also be considered. Study treatment groups will be compared within this model framework. All p-values will be interpreted in a descriptive manner.

The following subgroups will be analyzed:

- Gender
- Age
- Country
- US vs non-US
- Baseline MMS
- With/without previous biological or JAK inhibitors treatment
- Week 16 ABX464-NGlu AUC0-12 level above/below 7 000 h*ng/mL (vs. placebo)
- Concomitant UC medications.

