15.1.3. PRIMARY ANALYSIS OF PRIMARY EFFICACY VARIABLE

The primary efficacy analysis will be performed for FAS and PPAS.

The primary objective of this study is to determine an optimal ABX464 dose to be used in moderate to severe active ulcerative colitis patients who have failed or are intolerant to immunomodulators, Anti-TNF α , vedolizumab, JAK inhibitors and/or corticosteroids by comparing the mean change from baseline in the MMS at Week 8 for the three ABX464 dose levels to the placebo. An analysis of covariance (ANCOVA) model will be used to assess these changes.

The ANCOVA model for Change from Baseline MMS at Week 8 will include the fixed treatment effect, the previous use of biological or JAK inhibitors effect and the covariate, baseline MMS and a random error term.

The assumptions that the random errors in the ANCOVA model are normally distributed with homogeneity of variances will be checked. If either the hypothesis regarding normality of errors or the hypothesis of equal variances is rejected at the 5% significance level a nonparametric ANCOVA using the ranked data will be performed to test for differences in the mean change from baseline. The least square means and confidence intervals from the parametric ANCOVA will also be presented.

The dose testing will commence with comparing the ABX464 50mg dose with placebo. If this is significant at a 5% two-sided level (i.e. $p < 0.05$) a comparison against placebo will be carried out at the ABX464 100mg dose. Again, if significance at a 5% level for this test is observed the procedure will be repeated at the ABX464 25mg dose. If in this sequence of comparisons of ABX464 dose levels to placebo one is not significant (i.e., $p \geq 0.05$) the additional comparisons to placebo will not be

Document: \\iedc-vnasc01\BIOSdata\Abivax\ABX464\FZA92720\Biostatistics\Documentation\SAP\ABX464-103_SAP_V2.0_10MAY2021

Author: [REDACTED]

Version Number:
Version Date:

2.0
10May2021

Template No.: CS_TP_BS016 Revision 5

Reference: CS_WI_BS005

Effective Date: 01Apr2018

performed. Should any of these comparisons with the placebo treatment group be significant, further exploratory testing of the dose groups against each other will be conducted at the same significance level. A global comparison of all active treatment groups vs placebo group will also be conducted.

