15.2.1.6. Reduction Relative to Baseline in Stool Frequency and Rectal Bleeding

Number and percentage of patients in each Mayo stool frequency category will be summarized at every study visit and the number of patients with reduction in stool frequency sub-score relative to baseline will be recorded. The stool frequency sub-score corresponds to the **average** of the 3 most recent daily stool frequencies prior to the visit, rounded to the nearest whole number. The normal stool frequency is subtracted from this average to obtain the Mayo stool frequency sub-score for a particular visit. Frequency of stools will be obtained from e-Diaries completed daily by the patient.

Descriptive statistics for stool frequency sub-score and its change from baseline will be presented by visit.

Document: \\iedc-vnasc01\BIOSdata\Abivax\ABX464\FZA92720\Biostatistics\Documentation\SAP\ABX464-103_SAP_V2.0_10MAY2021

Author: [REDACTED] Version Number: 2.0
Version Date: 10May2021

Template No.: CS_TP_BS016 Revision 5

Reference: CS_WI_BS005

Effective Date: 01Apr2018

The frequency sub-score will be calculated as described above. Reduction relative to baseline is defined in Section 6.6.

Number and percentage of patients in each rectal bleeding category will be summarized. The number of patients indicating an improvement in rectal bleeding sub-score from the baseline rectal bleeding sub-score will be recorded. The rectal bleeding sub-score corresponds to the **worst category** of the 3 most recent values prior to the visit.

Only days when both the number of stool and the rectal bleeding are available will be considered for the calculation. If some data are missing from the most recent consecutive 3 days preceding the visit, then data from the next closest days within 7 days before the visit will be used for calculation.

15.2.1.7. Reduction Relative to Baseline in pMMS at every Visit and MMS at Week 16

Partial MMS will be assessed at every visit, and MMS at Screening, Week 8 and Week 16. Partial MMS is the sum of the stool frequency and rectal bleeding sub-scores of the MMS.

The screening MMS will be used as baseline MMS. Day 1 pMMS will be used as baseline pMMS. Absolute scores and change from baseline will be summarized by treatment arm, and the number of patients with a reduction relative to baseline in the scores will be recorded. Reduction relative to baseline is defined in Section 6.6

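### The MMS ANCOVA and MMRM leave out Day 1 pMMS, a more recent pre-dose measure of two of the three MMS components that the trial already collects; adding it is a nearly free gain in precision.

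*SAP*

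**What the plan says.** **Baseline for MMS.** SAP 15.1.1: "The MMS determined at screening will be used as baseline MMS, as MMS is not calculated at Day 1". SAP 15.2.1.7 repeats this and sets a different baseline for the symptom score: "The screening MMS will be used as baseline MMS. Day 1 pMMS will be used as baseline pMMS".

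**What is measured on Day 1.** Protocol 5.2.2 lists "Partial Modified Mayo Score" among the Day 1 procedures, with the first dose given at the site at that visit. SAP 15.2.1.6 builds the stool sub-score from the average "of the 3 most recent daily stool frequencies prior to the visit", and bleeding from the worst of the three most recent values before the visit. The Day 1 pMMS therefore describes the days before dosing.

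**Timing at screening.** Protocol 5.2.1 places the screening sigmoidoscopy "within 14 days prior to randomization/baseline" and allows the screening pMMS to be scored up to a week before that.

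**Models.** Besides treatment, the primary ANCOVA in SAP 15.1.3 has prior biologic or JAK inhibitor use and "the covariate, baseline MMS and a random error term". The MMRM in SAP 15.2.3.3 uses the baseline value of the variable being analysed, prior biologic or JAK inhibitor use, visit, and visit by treatment. SAP 7.1 lists baseline pMMS among the trial's covariates and leaves its use to the analysis sections. Neither MMS model takes it up.

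**The concern.** Patients enter on a screening MMS of 5 to 9, in a disease "which is characterized by a relapsing and remitting course". Some will have moved by Day 1, if only through regression to the mean after selection on a high score. The trial records that movement for two of the three components, and the MMS models do not use it.

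Two things are at stake. The first is precision: symptoms in the days before dosing should predict Week 8 symptoms at least as well as symptoms up to three weeks old, and adjusting for them also guards against a chance imbalance at Day 1. The second is reading the arm-level results: each arm's mean MMS change, and clinical response (at least 2 points and 30% from baseline, with a bleeding condition), run from screening and so include whatever happened before the first dose.

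**Working it through.** **1. Age of the screening symptom score.** At most 7 days (pMMS before endoscopy) + 14 days (endoscopy before randomisation) = 21 days. This is a ceiling, not a typical value.

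**2. The plan's own sample size.** Inputs from Protocol 9.4: reductions of 2.5 and 1.0 (difference 1.5), SD 2.1, two-sided 5%, two-sample t-test, 5% dropout, 58 per arm.
- Evaluable per arm: 58 × 0.95 = 55.1, so 55.
- SE of the difference: 2.1 × √(2/55) = 0.400.
- Power (noncentral t): 96.0% per comparison. Simulated joint power for all three gated tests is about 91%, which fits the stated target of more than 90%.
- Check: 55/0.95 = 57.9, so 58 per arm and 4 × 58 = 232 in total. The plan's figure is reproduced.

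**3. What the covariate could add.** If Day 1 pMMS explains a further fraction R² of residual variance, the SE becomes 0.400 × √(1 − R²). The documents give no correlations between screening, Day 1 and Week 8, so R² is an assumption. The planning SD of 2.1 is used as the reference throughout.

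| Extra R² (assumed) | SE at 55 per arm | Fall in SE | Power per test |
|---|---|---|---|
| 0 | 0.400 | – | 96.0% |
| 0.005 | 0.399 | 0.3% | 96.1% |
| 0.05 | 0.390 | 2.5% | 96.8% |
| 0.09 | 0.382 | 4.6% | 97.3% |
| 0.10 | 0.380 | 5.1% | 97.5% |

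Simulations with sub-score correlations of 0.6 to 0.8 (screening to Day 1), 0.4 to 0.5 (Day 1 to Week 8) and 0.3 to 0.4 (screening to Week 8) put R² between 0.005 and 0.09, depending on the other assumptions. At the top of that range the gain equals 1/0.91 = 1.10, about 10% more patients; at the bottom it is about 0.5%.

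**4. Is the placebo contrast affected?** In a separate simulation (55 per arm, 3,000 runs per scenario, assumed variances), all patients improved by 0, 0.5 or 1.0 point before dosing, and the improvement persisted.
- Mean placebo change from screening: −1.0, −1.5 and −2.0.
- Mean placebo change from Day 1 symptoms plus screening endoscopy: −1.0 each time.
- ANCOVA treatment difference with screening MMS as covariate: −1.5 each time.
- Rejection rate with no treatment effect: 4.5 to 5.5%, within simulation error of 5%.
- SE: 0.354 without Day 1 pMMS, 0.345 with it. The variance ratio is (0.345/0.354)² = 0.95.

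**5. Arm-level results.** One possible patient:

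| | Stool | Bleeding | Endoscopy | MMS |
|---|---|---|---|---|
| Screening | 2 | 2 | 2 | 6 |
| Day 1 | 1 | 1 | not done | – |
| Week 8 | 1 | 1 | 2 | 4 |

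MMS change is 4 − 6 = −2, or 2/6 = 33%, with bleeding at 1: a clinical responder. Change in pMMS from Day 1 is 2 − 2 = 0. This shows what can happen, not how often. Under the correlations in step 3, mean MMS falls 0.08 to 0.17 points before dosing, 4 to 9% of patients respond from screening but not from Day 1, and net response rates are 1 to 5 percentage points higher in every arm.

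**The case against.** The screening baseline is a stated and reasoned choice. SAP 6.2 takes the last value before first dose unless otherwise specified. The last full MMS is at screening, because there is no Day 1 endoscopy, and the last pMMS is on Day 1. One rule applied to two variables gives two baselines. The protocol points the same way for MMS, since section 9.2 plans "The change from screening in Modified Mayo scores and Partial Mayo scores during the study". This stands, and it is why the baseline definition should stay. It does not explain leaving a measured pre-dose covariate out of the model.

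The gain is small and power is already about 96% per test. That also stands: no conclusion need turn on this. Baseline pMMS may well be listed in SAP 7.1 only for the pMMS model, so its absence from the MMS models is not an internal contradiction.

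A reader might infer that improvement before the first dose is credited to the drug. The documents do not support that for the primary objective, which compares each dose with placebo. Pre-dose change is equal in expectation across randomised arms and cancels, as step 4 shows.

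A reader might also infer that the response comparison is materially diluted, or that baseline should be rebuilt from Day 1 symptoms and screening endoscopy. With a mean MMS difference near 1.5, simulated response differences were 30 to 31 points from screening and 31 to 32 from the composite, so dilution is about 1 point in 30. Response lies outside the gated sequence, and remission, endoscopic improvement and mucosal healing use no baseline. The composite has costs of its own. It mixes dates and departs from the score that qualified the patient. In simulation 6 to 8% of composite baselines fell below 5 and about 1% below 4, which fits none of the baseline MMS subgroups in SAP 7.5. Reasonable statisticians would differ on it.

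**Conclusion.** The point holds as a missed, low-cost improvement, not as a flaw in the primary comparison. The documents establish that Day 1 pMMS is collected before dosing, is more recent than the screening symptom score, and is absent from both MMS models. Treatment estimates and type I error are sound without it, and the planned power is met.

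The loss is about 0.5 to 9% of residual variance (0.3 to 4.6% of the SE), plus protection against chance Day 1 imbalance. That range rests entirely on assumed correlations, and the true value could lie outside it. MMS change and response within an arm should be read as change since screening. They can still be reconciled with pMMS change, because both symptom scores are recorded.

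**What to change.** Keep screening MMS as the defined baseline and change from it as the primary endpoint. Before unblinding, add Day 1 pMMS as a second baseline covariate in the MMS ANCOVA (SAP 15.1.3, including the rank-based fallback) and the MMS MMRM (SAP 15.2.3.3), and note this use in SAP 7.1. State a rule for a missing Day 1 pMMS so that no patient drops out of the model; the screening pMMS, as the last earlier value under SAP 6.2, would serve.

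Optional: tabulate screening-to-Day 1 change in stool and bleeding by arm, and report clinical response on the composite baseline (Day 1 stool + Day 1 bleeding + screening endoscopy) as a supportive sensitivity analysis only, not as a replacement.

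Cost: a few lines of SAP text, one degree of freedom per model, and no new data. The optional response analysis would show slightly lower rates in all arms.
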